3.2 Secondary Objectives and Endpoints

Secondary Objectives

- Evaluate the safety and tolerability of GSK1265744 (daily oral 744 + 744LA) for 76 weeks of follow-up after final injection (each cohort will be analyzed separately)
- Evaluate the safety and tolerability of oral 744 from Week 0 to Week 5

- Evaluate the pharmacokinetics of 744LA administered as 800 mg IM every 12 weeks for 52 weeks of follow-up after final injection
- Evaluate differential pharmacokinetics of 744LA in participants by age, gender, race, ethnicity, weight, body mass index (BMI), and smoking status
- Evaluate the acceptability of 744LA injections
- Evaluate the effect of 744LA on sexual risk behavior by change from enrollment for repeat assessments to during the study period
- Evaluate HIV incidence and antiretroviral drug resistance, if any participants acquire HIV infection during the study
- Evaluate the safety, tolerability and pharmacokinetics of 744LA in the subset of women who use a hormone-based contraceptive

Secondary Endpoints

- Proportion of participants who discontinue either oral or injectable study product for reasons of toxicity, tolerability, or acceptability prior to completion of the full oral and injectable phases
- Proportion of participants experiencing Grade 2 or higher clinical AEs and laboratory abnormalities during 52 weeks following final injection (safety) and any AE that leads to discontinuation (tolerability) during the aggregate oral and injectable phases
- Proportion of participants experiencing Grade 2 or higher clinical AEs and laboratory abnormalities (safety) and any AE that leads to discontinuation (tolerability) in the oral phase and washout period
- Plasma drug levels of GSK1265744 at designated time points after each injection of 744LA (by cohort only)
- Plasma drug levels of GSK1265744 at designated time points after each injection of 744LA stratified by age, gender, race, ethnicity, weight, BMI, and smoking status
- Proportion of participants willing to use an injectable agent such as the study product for HIV prevention in the future
- Change from enrolment of self-reported sexual behaviour (number of sexual partners, episodes of unprotected anal and/or vaginal intercourse) during the study period using a standardized assessment tool (in aggregate only)
- Number of incident HIV infections through the study period, including number with treatment emergent resistance

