- Proportion of injectable hormonal-contraception-using female participants who reach a safety or tolerability endpoint as defined above

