9.7.1 Association between Pharmacokinetics and Baseline Characteristics

To evaluate differential pharmacokinetics of 744LA in participants by age, gender, race, ethnicity, weight, body mass index (BMI), and smoking status, we will use GEE regression model to account the correlations of the PK parameters following three injections in Cohort 1 or five injections in Cohort 2. The analysis will be performed separately for each cohort. The associations between the PK parameters and the predictors will be tested in univariate models (include one predictor in each model) and

in a multivariate model (include all predictors). Each model will be adjusted for sites (US vs. Non-US sites) by cohort.

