9.11 HIV Incidence

HIV incidence rate will be calculated as the total number of participants with confirmed HIV infection during study follow-up divided by the person-years accumulated in each arm. 95% CIs will be calculated based on Poisson distribution assumptions. In addition, exact tests based on the Poisson distribution will be used to compare HIV incidence rate between the treatment arms.

9.12 Evaluate the Safety, Tolerability and Pharmacokinetics of 744LA in the Women Who Use Injectable Hormonal Contraception

The safety and tolerability analyses described above will be performed on the subset of female participants who self-report the use of injectable hormonal-based contraception at study entry or at any time during the study period. Proportions of such women meeting safety or tolerability endpoints will be compared a) across treatment arms b) to the women in the 744LA arm who are do not report use of injectable hormonal contraception c) to the overall study population randomized to active GSK1265744. The comparisons in a) are to evaluate the safety and tolerability of the 744LA injection in the women who report use of injectable hormonal-based contraception between the two treatment arms. The comparisons in b) are to evaluate the safety and tolerability of the 744LA injection between the women who report the use of injectable hormonal-based contraception and the women who are do not report the use of injectable hormonal-based contraception. The comparisons in c) are to evaluate the safety and tolerability of the women who report the use of injectable hormonal-based contraception in contrast to the rest of the enrolled participants in the study. All comparisons will be done using the Fisher exact test. The data will be analyzed by cohort and in aggregate.

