11.3 Pharmacokinetic and Other Secondary Analyses

11.3.1 List of Tables

Table 21 Summary of pharmacokinetic parameters by injection

Table 22 Assess the time to steady state of the plasma drug concentration, C_{τ}

Table 23 Associations of sex at birth (or BMI) with pharmacokinetic parameters

Table 24 Change in sexual risk behavior (number of sexual partners) from baseline

Table 25 HIV incidences during the study

Table 26 Reported pregnancies by treatment arm and cohort

Table 27 The proportion of women experiencing any Grade 2 or higher AEs (a) prior to completion of the full oral phase and (b) prior to completion of the full injection phase --- among the women who use any injectable hormonal contraception (combined cohort)

Table 28 The proportion of the women who discontinue the study product for reasons of toxicity, tolerability, or acceptability (a) prior to completion of the full oral phase and (b) prior to completion of the full injection phase—among the women who use any injectable hormonal contraception

Table 29 Summary of pharmacokinetic parameters by injection and cohort —among the women who use any injectable hormonal contraception

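### The secondary objective and the title of SAP 9.12 cover 744LA pharmacokinetics in women using hormonal contraception, but no PK analysis follows and no user versus non-user exposure estimate is planned

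*SAP*

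**What the plan says.** SAP 3.2 lists as a secondary objective "Evaluate the safety, tolerability and pharmacokinetics of 744LA in the subset of women who use a hormone-based contraceptive". The title of SAP 9.12 repeats pharmacokinetics, for women using injectable hormonal contraception.

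The matching endpoint in 3.2 is a proportion only: "Proportion of injectable hormonal-contraception-using female participants who reach a safety or tolerability endpoint as defined above".

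The text of 9.12 begins "The safety and tolerability analyses described above will be performed on the subset of female participants" and defines the subset by self-reported use of injectable hormonal contraception at entry or at any time on study. It sets up three contrasts, starting with "Proportions of such women meeting safety or tolerability endpoints will be compared a) across treatment arms". The second sets users against women in the 744LA arm who do not report use; the third sets users against the active group overall. It then fixes the test: "All comparisons will be done using the Fisher exact test".

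SAP 9.7.1 names its PK predictors: "To evaluate differential pharmacokinetics of 744LA in participants by age, gender, race, ethnicity, weight, body mass index (BMI), and smoking status". It also states "Each model will be adjusted for sites (US vs. Non-US sites) by cohort" and fits the cohorts separately. Contraceptive use is not among the predictors.

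The only PK output for the subset is "Table 29 Summary of pharmacokinetic parameters by injection and cohort", limited to women using injectable hormonal contraception.

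**The concern.** The objective has three components: safety, tolerability and pharmacokinetics. SAP 9.12 gives the first two a method and a comparison with non-using women on 744LA. The third appears in the title and then drops out of the text.

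What is at stake is whether the trial can say anything quantitative about exposure in this subset. As planned, it ends with summary statistics in users and nothing to set them against. Any comparison devised after unblinding would be post hoc.

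**Working it through.** **Looking for a PK contrast anywhere in the SAP**

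| Place in SAP | What it plans | User versus non-user PK? |
|---|---|---|
| 9.3 | Tests for continuous variables between treatment arms, or between time points within an arm | No |
| 9.7 | AUC(0-tau), Cmax and C-tau compared across injection intervals within participants; time to steady state | No |
| 9.7.1 | GEE on age, gender, race, ethnicity, weight, BMI and smoking, adjusted for US vs non-US, by cohort | No |
| 9.12 | Three contrasts of safety and tolerability proportions | No PK |
| 9.13 | Exploratory PK against the same seven demographic variables, or PD endpoints | No |
| Table 21 | PK parameters by injection; as listed, not split by sex or contraceptive use | No |
| Table 23 | PK by sex at birth or BMI | No |
| Table 29 | PK parameters in users, by injection and cohort | Users only |

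No section supplies the contrast. Table 21 cannot serve as the reference for Table 29, because as listed it mixes men, users and non-using women.

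**Would the contrast be worth reporting?**

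The SAP states no precision figure for this subset, so there is nothing to reproduce. The following is for scale only.

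Inputs from the SAP: 82 participants on active product in Cohort 1 and about 66 in Cohort 2 (2.4); about 60% women (4.1).
- Women on active product: 0.60 × 82 ≈ 49 and 0.60 × 66 ≈ 40, together 89.
- These are randomized counts. The injected PK population can only be the same size or smaller.

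Assumptions not in the SAP: 20-60% of these women are users; between-subject CV 40-80%; one value per woman; normal approximation.

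Formulas:
- SD of log parameter = √ln(1 + CV²): 0.385 at CV 40%, 0.703 at CV 80%.
- SE of log ratio = SD × √(1/users + 1/non-users).
- 95% CI = estimate ×/÷ exp(1.96 × SE).

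| Women on 744 | Best case: CV 40%, 40% or 60% users | Worst case: CV 80%, 20% users |
|---|---|---|
| Cohort 1, 49 | 20 v 29: SE 0.112, factor 1.25 | 10 v 39: SE 0.249, factor 1.63 |
| Cohort 2, 40 | 16 v 24: SE 0.124, factor 1.28 | 8 v 32: SE 0.278, factor 1.72 |
| Combined, 89, cohort in model | 36 v 53: SE 0.083, factor 1.18 | 18 v 71: SE 0.186, factor 1.44 |

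An estimated ratio of 1.00 in Cohort 1 would thus carry an interval of 0.80 to 1.25 at best and 0.61 to 1.63 at worst. That could exclude a large change in exposure but not a modest one.

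**Who is a user?**

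The objective speaks of hormone-based contraception; 9.12 and Tables 27-29 speak of injectable hormonal contraception. If non-users are simply all other women, users of other hormonal methods fall into the reference group. Because 9.12 counts use at any time, a woman who starts late is a user for every injection interval. The SAP does not show whether dates of use are recorded.

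**The case against.** The best defence is that the objective is not comparative. Where the SAP wants a PK contrast it says so: a separate objective in 3.2 asks for differential PK by demographic factors, and 9.7.1 carries it out. For contraceptive users it asks only for an evaluation in the subset, the listed endpoint is a safety or tolerability proportion, and Table 29 provides a description. This has force: the user versus non-user ratio is an addition, and the plan does not break a stated promise to estimate it. But 9.12 itself treats the same objective as calling for a comparison with non-using women for safety and tolerability. PK alone is left without one, and the section's text does not even point to Table 29.

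Three stronger readings are tempting and are not supported:
- *The Fisher sentence is an error.* It follows three contrasts of proportions and refers to them. Nothing assigns that test to AUC, Cmax or C-tau. The fault is a missing PK sentence.
- *The gender coefficient in 9.7.1 and Table 23 is confounded.* Contraceptive use follows from sex and does not cause it, so a coefficient without it remains a valid total sex difference. Adding the term would change the question to men versus non-using women. With an assumed user ratio of 0.80 and 20-40% use, the share of the female/male ratio passing through contraception would be 0.80^0.2 = 0.956 to 0.80^0.4 = 0.915. Both inputs are assumed, and the share vanishes if use has no PK effect.
- *The trial singles out contraception as an influence on exposure.* The SAP names the subset and gives no reason for it.

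**Conclusion.** The point holds as a mismatch between objective, section title, method and output. PK in women using hormonal contraception is named twice, 9.12 specifies no analysis of it, and the single table has no comparator. The plan yields no estimate or interval for exposure in users versus non-users.

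This rests on the text alone. The interval factors above (1.25 to 1.63 in Cohort 1, 1.28 to 1.72 in Cohort 2) depend on assumed user shares and CVs. They describe what an added analysis could deliver, not harm done by the current plan. The matter concerns one secondary objective in a subset and does not touch the primary safety and tolerability analyses. It is a cheap improvement that should be made before the analysis.

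**What to change.** - **SAP 9.12.** Add a PK paragraph: among women in the 744 arm, compare log AUC(0-tau), Cmax and C-tau between users and non-users of injectable hormonal contraception, with the 9.7.1 GEE and its covariates except gender. Report the geometric mean ratio with its 95% CI by cohort, in keeping with 9.7.1. Any combined estimate should be supportive and adjusted for cohort.
- **Definition of use.** Keep the 9.12 definition. Classify by dosing interval only if dates of use are recorded.
- **Table 29.** Add a column for non-using women on 744, and the ratio with its interval.
- **Objective versus method.** Reconcile hormone-based contraception in 3.2 with injectable contraception in 9.12 and Tables 27-29, and state where users of other hormonal methods go, so that they do not enter the reference group unnoticed.

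The Fisher sentence can stay.

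The cost is one paragraph, one term in a model already planned, and one table column. The downside is wide intervals in a small subset, from a comparison that is not randomized and should be labelled as such.

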2.4 Schema

Cohort 1

W = Week

Cohort 2

The 110 participants in Cohort 1 and 90 participants in Cohort 2 were randomized to one of the two study arms with an active GSK 744 to placebo ratio of 3:1, stratified by gender and region (US and non US), as follows:

Cohort 1

Arm 1: 82 participants received daily oral 744 (30 mg tablets) for 4 weeks, followed by an one week washout period, to establish safety and tolerability, followed by intra-muscular (IM) gluteal injections of 800 mg of 744LA (administered as two sequential 400 mg gluteal injections) at three time points at 12 week intervals as: Week 5, Week 17, and Week 29.

Arm 2: 28 participants received daily oral matching placebo and IM injections of vehicle-matched placebo on the same schedule as Arm 1.

Cohort 2

Arm 1: Approximately 66 participants will receive daily oral 744 (30 mg tablets) for 4 weeks, followed by a one week washout period, to establish safety and tolerability, followed by intra-muscular (IM) gluteal injections of 600 mg of 744LA (administered as one 600 mg gluteal injection) at five time points at 4 and 8 week intervals as: Week 5, Week 9, Week 17, Week 25, and Week 33.

Arm 2: Approximately 22 participants will receive daily oral matching placebo and IM injections of vehicle-matched placebo on the same schedule as Arm 1.

All participants will receive HIV testing with pre- and post-test counseling, in addition to risk-reduction counseling and condoms and lubricant. All participants will be followed according to the Schedule of Evaluations and Procedures provided in HPTN077 protocol Appendices I-IV.

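### SAP 9.12 tests the non-randomised contraception contrasts (b) and (c) with an unadjusted Fisher test, so any regional or sex differences in use and AE rates would show as a contraception difference

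*SAP*

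**What the plan says.** Section 9.12 applies the safety and tolerability analyses to women "who self-report the use of injectable hormonal-based contraception at study entry or at any time during the study period". It then compares the proportions meeting a safety or tolerability endpoint in three ways:

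- (a) active against placebo, among users;
- (b) users against non-user women on active product, worded as "to the women in the 744LA arm who are do not report use of injectable hormonal contraception";
- (c) users against a wider comparator, given first as "to the overall study population randomized to active GSK1265744" and later in the same section as "in contrast to the rest of the enrolled participants in the study".

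The method is one sentence: "All comparisons will be done using the Fisher exact test". On grouping it adds only "The data will be analyzed by cohort and in aggregate". Region and gender are not mentioned.

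Elsewhere the SAP does allow for region. It is a randomisation stratum together with gender (2.4, 4.7). In the PK covariate models of 9.7.1, "Each model will be adjusted for sites (US vs. Non-US sites) by cohort". The SMSQc (9.8) and baseline acceptability (9.9) comparisons also have a site-adjusted model. Section 9.3 offers logistic regression when covariates need adjusting, and 9.4 adjusts for US versus non-US if the regions differ, but both are written for comparisons between the two treatment arms.

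**The concern.** Contraceptive use is chosen by the participant. Stratified randomisation balances active and placebo within gender and region. It does nothing to balance users against non-users inside the active arm. The sites are in the US, Brazil and sub-Saharan Africa (4.6), and both contraceptive practice and the recording of Grade 2 events may vary between them. If both do, (b) mixes a regional difference with a contraceptive one. In (c) every user is a woman while the comparator includes men, so a sex difference in AE rates alone is enough to shift the result.

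Safety, tolerability and PK in women using hormonal contraception is a secondary objective (3.2). A confounded contrast could suggest a problem that is not there or hide one that is, because the bias can run either way. It affects the estimate whether or not the p-value falls below 0.05.

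**Working it through.** The SAP states no sample size, power or alpha for these contrasts, so there is no planned figure to reproduce. The check asks how often Fisher rejects when contraception has no effect.

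**Inputs from the SAP.** Active arms: 82 (Cohort 1) + about 66 (Cohort 2) = 148. About 60% women (4.1): 0.6 × 148 ≈ 89 women, leaving 59 men.

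**Assumptions, because the SAP gives none of these.** Half the women are non-US (45 US, 44 non-US). Use by region and AE rates by region and sex are varied. Two-sided test at 0.05. Users and comparators are all taken from the active arm; for (c), the comparator is every other active participant.

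**Expected spurious difference in (b)** = (non-US share among users − non-US share among non-users) × (non-US AE rate − US AE rate). With equal regional halves:

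- Use 10% US / 50% non-US: 0.50/0.60 − 0.50/1.40 = 0.833 − 0.357 = 0.476.
- Use 5% / 60%: 0.60/0.65 − 0.40/1.35 = 0.923 − 0.296 = 0.627.

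Multiplying by the regional AE gap, and simulating the tests with 45 + 44 women (ranges are across repeat runs):

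| Use US / non-US | AE US / non-US | Spurious difference | Fisher rejects |
|---|---|---|---|
| 10% / 50% | 80% / 70% | −4.8 points | 6–7% |
| 10% / 50% | 80% / 60% | −9.5 | 12–13% |
| 10% / 50% | 80% / 50% | −14.3 | 21–23% |
| 5% / 60% | 80% / 70% | −6.3 | 8% |
| 5% / 60% | 80% / 60% | −12.5 | 20% |
| 5% / 60% | 80% / 50% | −18.8 | 37–38% |

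A Mantel-Haenszel test stratified by US/non-US rejects about 4–6% of the time in these settings, or 2–3% with a continuity correction.

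**No-bias cases.** Both links are needed. With use 30% in both regions and AE 85% / 55%, Fisher rejects 2.5%. With use 10% / 60% but AE 70% everywhere, it rejects 3.6%. At the other extreme, use 5% / 80% with AE 85% / 55% gives 62.7%.

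**Sex in (c).** Take use 30% in both regions (27 users, 62 non-user women), no regional gap, AE 65% in women and 85% in 59 men. The comparator rate is (62 × 0.65 + 59 × 0.85)/121 = 90.45/121 = 74.8%, against 65% in users: a 9.8-point gap due to sex alone. Fisher rejects 15.4% for (c) and 3.4% for (b).

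**Are two region strata enough?** Not always. Assume 45 US, 22 Brazilian and 22 sub-Saharan African women, use 10/10/70% and AE 80/80/50%. Within the non-US stratum, the sub-Saharan share is 15.4/17.6 = 0.875 among users and 6.6/26.4 = 0.25 among non-users. That leaves a residual 0.625 × (−30) = −18.8 points. The US/non-US Mantel-Haenszel test still rejects about 21% (14% corrected). With a sub-Saharan rate of 60% it rejects about 12% (7% corrected). Three strata bring this to about 5% (2% corrected).

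**The case against.** **Both links are unproven.** The SAP gives neither contraceptive use nor AE rates by region, nor the regional split of the women. A reader might infer that 9.12 will produce a false contraception effect. The document does not support that: without a use gap or without an AE gap, Fisher is at or below its nominal level. This stands, and it is why the point is conditional.

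**The contrasts carry limited weight.** The matching secondary endpoint (3.2) is a proportion in users alone. Tables 27 to 29 (11.3.1) report users only, and 9.12 never claims a causal effect. This too stands. It lowers the importance of the point but does not remove it, because the text of 9.12 still pre-specifies the tests.

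**Contrast (c) may be a deliberate whole-population benchmark**, in which a sex difference is part of what is compared. That is a fair reading, so including men is not in itself an error. It argues for presenting (c) descriptively, since a p-value invites a reading about contraception.

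**Plain Fisher is the SAP's convention for binary endpoints** (9.5.5, 9.6), and not every repeated-measures model is site-adjusted. True, but those comparisons are between randomised arms, where leaving out region does not bias the contrast in this way.

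**Sections 9.3 and 9.4 might be thought to allow adjustment.** They are worded for treatment-arm comparisons, and the sentence on the test in 9.12 covers all three contrasts.

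**Conclusion.** The point holds in conditional form. Section 9.12 fixes an unadjusted test for two non-randomised contrasts, and nothing else in the SAP repairs this. For (b), bias arises only if use and AE rates both differ by region. For (c), a sex difference in AE rates is sufficient. Under no true effect the false-positive rate for (b) is about 3% with no use gap and about 38% with use 5%/60% and AE rates 80%/50%; the more extreme setting above goes higher. All of these figures rest on assumed rates, an assumed half-and-half regional split and about 89 active-arm women. The primary analysis and contrast (a) are not affected by this point.

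**What to change.** In 9.12:

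- Keep the Fisher exact test for (a) only.
- For (b), use an exact conditional or Mantel-Haenszel analysis stratified by region (US, Brazil, sub-Saharan Africa where numbers allow, otherwise US/non-US), and also by cohort in the aggregate analysis. Report a common risk difference or odds ratio with its 95% CI.
- For (c), report the proportions descriptively as a whole-population benchmark without a test, or stratify by gender and region. Restricting (c) to active-arm women and removing the users from the comparator would only repeat (b). State one comparator: the overall active population contains the active users themselves, while the rest of the enrolled participants would, as worded, bring in placebo.
- State that (b) and (c) are observational, and that stratifying by region does not deal with age or other differences.

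A parallel user/non-user contrast in placebo women would not serve as a control: (28 + 22) × 0.6 = 30 women, or about 9 users at an assumed 30% use.

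The cost is SAP wording and a few lines of code, with slightly less power if region turns out not to be a confounder. Data collection and the primary analysis do not change.
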